^f **Physical Examination:** To be performed at screening, then prior to study treatment administration on Day 1, Day 8, Day 15 and Day 22 of Cycle 1, within 24 hours prior to study treatment administration on Day 1 of each subsequent cycle, and at the EOT visit. Consists of examination of major body systems, including neurological, digestive exam, respiratory (signs and symptoms, respiratory rate), hepatic and spleen span, lymph node examination, weight and height (height at baseline only). Only main diagnoses will be reported in the eCRF as AEs or medical history. Signs and symptoms related to multiple myeloma ongoing at baseline will be recorded in medical history and will be reported in AE page in case they worsen or become serious during study treatment. Laboratory abnormalities at baseline will be recorded in laboratory pages.

- g* **Vital Signs:** Blood pressure, heart rate and temperature required at screening and then on Day 1, Day 8, Day 15 and Day 22 of Cycle 1 in both arms. For subsequent cycles vital signs are to be taken on Day 1 of each cycle in both arms. In addition, in the IPd arm, vital signs are to be taken just before starting infusion and 1 hour after starting infusion and end of infusion on Day 1, Day 8, Day 15 and Day 22 of Cycle 1 and Day 1 and Day 15 of each subsequent cycle up to and including Cycle 4 and as clinically indicated. The final measurements will be performed at the EOT visit in both arms.
- h* Includes HBsAg, anti-HBsAb, and anti-HBcAb (total and IgM) and HBV DNA in case of positive anti-HBsAg (see [Section 8.2.5](#)). Once at any time if HBV status unknown before treatment started and to be repeated if clinically indicated for patient still on treatment at the time of amended protocol 07.
- i* **12-Lead ECG:** To be performed at screening, C2D1 (pre-dose), EOT, and as clinically indicated.
- j* **ePRO (EORTC QLQ-C30, MY20 and EQ-5D-5L):** To be completed by the patient at the center prior to discussing their health/disease status, and prior to study treatment administration, or other study-related procedures on Day 1 of every cycle, at the EOT visit, and 60 days (± 5 days) after last study treatment administration. The time estimated to complete the EORTC QLQ-C30 is approximately 10-15 minutes. The time estimated to complete the MY20 and EQ-5D-5L is approximately 5-10 minutes.

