3 LIST OF ABBREVIATIONS

ADA:	antidrug antibodies
ADCC:	antibody-dependent cellular-mediated cytotoxicity
AEs:	adverse events
AESI:	adverse event of special interest
ALT:	alanine aminotransferase
ANC:	absolute neutrophil count
ASCO:	American Society of Clinical Oncology
ASCT:	autologous stem cell transplantation
AST:	aspartate aminotransferase
AT:	all treated
AUC:	area under the curve
BM:	bone marrow
BMA:	bone marrow aspirate
cADPR:	cyclic adenosine-diphosphate-ribose
CBR:	clinical benefit rate
CDC:	complement-dependent cytotoxicity
CI:	confidence interval
CID:	clinical important difference
CLL:	chronic lymphocytic leukemia
CR:	complete response
DMC:	Data Monitoring Committee
DOR:	duration of response
DVT:	deep vein thrombosis
ECOG:	Eastern Cooperative Oncology Group
ELISA:	enzyme linked immunoabsorbant assay
EORTC:	European Organisation for Research and Treatment of Cancer
EOT:	end of treatment
ePROs:	electronic patient reported outcomes
EQ-5D-5L:	European Quality of Life Group questionnaire with 5 dimensions and five levels per dimension
FCBP:	female of child-bearing potential
FISH:	fluorescence in situ hybridization
FPI:	first patient in study
GVHD:	graft versus host disease
HBcAb:	hepatitis B core antibody
HBsAb:	hepatitis B surface antibody
HBsAg:	hepatitis B surface antigen
HBV:	hepatitis B virus
HDAC:	hystone deacetylase
HLA:	human leukocyte antigen
HLGT:	high level general term

HLT:	high level term
HRQL:	health-related quality of life
HSC:	hematopoietic stem cell
IAR:	infusion associated reaction
ICF:	informed consent form
IEC:	independent ethics committee
IFN:	interferon
IL:	interleukin
IMiDs:	immunomodulatory drugs
IMWG:	International Myeloma Working Group
IPd:	isatuximab pomalidomide dexamethasone
IRB:	institutional review board
IRC:	Independent Response Committee
IRT:	interactive response technology
ITT:	intent-to-treat
IV:	Intravenous
kDa:	kilodalton
KIR:	killer cell inhibitory receptor
mAb:	monoclonal antibody
MedDRA:	Medical Dictionary for Regulatory Activities
MM:	multiple myeloma
MR:	minimal response
MRD:	minimal residual disease
NAD+:	nicotinamide adenine dinucleotide
NCI-CTCAE:	National Cancer Institute Common Terminology for Adverse Event
NK:	natural killer
NSAIDs:	non steroid anti-inflammatory drugs
ORR:	overall response rate
OS:	overall survival
PBMC:	peripheral blood mononuclear cells
Pd:	pomalidomide dexamethasone
PD:	progressive Disease
PDy:	pharmacodynamic
PE:	pulmonary embolism
PFS:	progression free survival

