8.2.5 Other toxicities

For \geq Grade 3 adverse reactions, except fatigue, local reaction, fluid retention, anemia and other reactions that do not cause serious morbidity, study treatment should be held for a maximum of 2 weeks from the planned date of next cycle until improvement to \leq Grade 1, then reinstated, if medically appropriate. A reduction of subsequent doses will be left to the Investigator's judgment.

Guidance in case of hepatitis B reactivation occurring under study treatment

Patient still on treatment at the time of amended protocol 07 will be tested for HBV serology and HBV viral DNA once at any time if HBV status was unknown before treatment started; test will be repeated if clinically indicated.

In case of viral reactivation during study treatment (greater than 1 log₁₀ IU/mL increase in HBV DNA or reappearance of hepatitis B surface antigen [HBsAg] or detection of HBV DNA in patients with resolved infection) study treatment will be held and specialist consulted for initiation of anti-viral treatment and monitoring of the patient. Resolved infection means previous known history of acute or chronic hepatitis B or the presence of total anti-hepatitis B core antibody

(HBcAb) with/without anti-hepatitis B surface antibody (HBsAb); HBsAg negative; undetectable serum HBV DNA; and normal ALT levels. Restart of study treatment should be agreed between the Sponsor, the Investigator and specialist (hepatologist) if infection is controlled. ALT and AST will be closely monitored every month up to study treatment discontinuation. HBV DNA to be done as per specialist advice.

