10.1.6 Post PFS study cut-off date

Patients still on treatment at the PFS cut-off date will continue study treatment until at least 1 treatment discontinuation criterion as defined in [Section 10.3.2](#) is met. The following information will be collected during the study treatment administration:

- Study treatment administration.
- Physical examination: main diagnoses to be reported in the eCRF as AEs and newly occurring laboratory abnormalities to be recorded in laboratory pages.
- Vital signs including blood pressure, heart rate and body temperature. In addition in IPd arm, prior to start of each isatuximab infusion, 1 hour after start of each infusion and at the end of each infusion on Day 1 and on Day 15 up to and including cycle 4 and as clinically indicated.
- ECOG PS.
- Concomitant medications used throughout the cycle.
- Second primary malignancies.

- Patient diaries for oral study treatment (dexamethasone when taken orally and pomalidomide; except for study treatment doses administered by the study nurse/doctor).
- AE assessment: all related AEs and all serious AEs (regardless of relationship to study treatment) ongoing at the time of cut-off will be followed until resolution or stabilization. All new related AEs (regardless of seriousness) will be collected and followed until resolution or stabilization.

Disease assessment

- Only overall response according to assessment per Investigator and based on local laboratories and local reading of radiological assessment will be collected.
- Bone marrow aspirate (or biopsy as clinically indicated):
 - Bone marrow plasma cell infiltration (local laboratory) to confirm CR, and as clinically indicated,
 - BMA for MRD assessment in case of CR (central laboratory).

Local laboratory assessments

- In case of viral reactivation during study treatment (greater than 1 log₁₀ IU/mL increase in HBV DNA or reappearance of HBsAg or detection of HBV DNA in patients with resolved infection), ALT and AST will be closely monitored every month up to study treatment discontinuation. HBV DNA to be done as per specialist advice.

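### Flow-chart footnote h makes the HBV DNA test conditional on an undefined marker, while Section 8.2.5 requires it unconditionally in the same patients

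*Protocol*

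**What the plan says.** Two current texts, both listed as changed in the amendment 07 summary, govern the first hepatitis B work-up.

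- **Section 1.2, footnote h.** It lists HBsAg, anti-HBsAb and anti-HBcAb (total and IgM), then adds "HBV DNA in case of positive anti-HBsAg", with a pointer to Section 8.2.5. On who and when: "Once at any time if HBV status unknown before treatment started and to be repeated if clinically indicated for patient still on treatment" when amendment 07 takes effect.
- **Section 8.2.5.** Patients on treatment at amendment 07 "will be tested for HBV serology and HBV viral DNA once at any time if HBV status was unknown before treatment started". No serological result is set as a condition for the DNA test.

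Section 8.2.5 then uses HBV DNA in its definitions. Resolved infection requires, among other things, "undetectable serum HBV DNA". Reactivation is any of three findings: a DNA rise of more than 1 log10 IU/mL, reappearance of HBsAg, or "detection of HBV DNA in patients with resolved infection". On reactivation, study treatment is held and a specialist consulted.

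Sections 10.1.6 and 10.1.7 repeat the reactivation definition and otherwise say only "HBV DNA to be done as per specialist advice".

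**The concern.** The footnote and the section it points to give different conditions for the same test in the same patients at the same time. Section 10.1 requires patients to be evaluated according to the flow charts, and the protocol sets no order of precedence, so a site that follows the footnote is following the protocol.

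For these patients this is the first HBV work-up that the protocol orders. Exclusion criterion E 21 covers only known active hepatitis, and the screening procedures in Section 10.1.1 contain no HBV test. Reactivation risk is also the stated reason for amendment 07.

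A site working from the footnote would lack a reference DNA value in some or all HBsAg-negative, anti-HBc-positive patients. It could not confirm that they meet the definition of resolved infection. It would have no starting point for a log10 rise, and a later detectable DNA could not be read against a known undetectable value. Those judgements decide whether study treatment is held.

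**Working it through.** The plan states no figure to reproduce. The check compares the two texts and then counts what each one orders.

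**1. Same patients, same timing.** Both texts cover patients still treated at amendment 07 whose HBV status was unknown before treatment. Both order one test at any time, repeated if clinically indicated. Only the DNA condition differs.

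**2. What the footnote's marker can mean.** The footnote's assay list has HBsAg, anti-HBsAb and anti-HBcAb. Section 3 defines HBsAg, HBcAb and HBsAb ("hepatitis B surface antibody"). The term anti-HBsAg is in neither list. It is either a slip for the antigen, HBsAg, or a second name for the antibody, anti-HBs. DNA testing is conditional on both readings, so correcting the label alone would not remove the conflict.

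**3. Count by serological pattern.** HBsAg, anti-HBc and anti-HBs, each positive or negative, give 2 × 2 × 2 = 8 patterns. The anti-HBc-based description of resolved infection in Section 8.2.5 (HBsAg negative, anti-HBc positive, anti-HBs either way) covers 2 of these.

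| Rule | DNA taken, all 8 patterns | DNA taken, 2 resolved-type patterns |
|---|---|---|
| Section 8.2.5 | 8 | 2 |
| Footnote h, label = HBsAg | 4 | 0 |
| Footnote h, label = anti-HBs | 4 | 1 |

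On the anti-HBs reading, 2 of the 4 HBsAg-positive patterns (those without anti-HBs) also go untested for DNA. These are counts of patterns, not of patients. They show where the rules diverge, not how often.

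**4. Does other text reconcile the rules?** The amendment summary speaks only of additional viral serology. Sections 10.1.6 and 10.1.7 deal with follow-up after reactivation and leave DNA testing to the specialist. Neither says when the first DNA test is taken.

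**5. Size of the group, for illustration.** The documents give neither the number still on treatment nor the date of first patient in. I take the design assumptions of Section 11.1: 150 patients per arm, 15 patients per month (20 months for 300), exponential PFS with medians of 4 and 6.67 months. I use PFS as a proxy for time on treatment. With T months from first patient in to 26 November 2020 and λ = ln 2 / median, the expected number still progression-free in an arm is

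150 × [exp(−λ(T − 20)) − exp(−λT)] / (20λ).

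| Assumed first patient in | T (months) | Pd | IPd | Total |
|---|---|---|---|---|
| September 2016 | 50.8 | 0.2 | 2.6 | about 3 |
| January 2017 | 46.8 | 0.4 | 3.9 | about 4 |
| July 2017 | 40.9 | 1.1 | 7.2 | about 8 |

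The number would be higher if PFS ran longer than assumed. Only those with unknown HBV status, and among them those whose pattern falls in the gap, are affected.

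**The case against.** The strongest case on the other side is about weight.

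- **The pointer.** The reference to Section 8.2.5 directly follows the disputed condition, so a careful site would read both. That lowers the chance of error. But the reader who follows it meets a different rule and is not told which governs.
- **The label.** HBsAg with a stray prefix is the more natural reading, since the footnote also writes anti-HBsAb and anti-HBcAb. If so, the anti-HBs row of the first table falls away. What remains is the reading under which neither resolved-type pattern gets a DNA value.
- **The log10 criterion.** On that reading HBsAg-positive patients do get a DNA value, so a rise can still be assessed in them. The main loss is then detection in resolved infection. This is fair.
- **No pre-treatment value either way.** Section 8.2.5 itself asks for one test during treatment. True, but that test still supplies the reference value its definitions need.
- **Remaining safeguards.** HBsAg reappearance, repeat testing when clinically indicated, and ALT and AST on Day 1 of each cycle (footnote l, Section 10.1.6) all continue. Detection is weakened, not lost. After the final OS cut-off, however, Section 10.1.7 leaves management to local practice and specifies monthly ALT and AST only once reactivation has occurred.
- **Intent.** The amendment summary and the flow-chart row title mention only serology, which would fit serology first with DNA as a reflex test. That is possible, but Section 8.2.5 says otherwise, and a reflex rule tied to HBsAg would not support its definition of resolved infection.

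**Conclusion.** The concern holds. The conflict is plain on the face of the two texts, stands under either reading of the undefined marker, and is resolved nowhere else in the protocol. Followed as written, the footnote omits HBV DNA in one or both of the two resolved-type patterns, where Section 8.2.5 requires it in both.

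The practical size is modest. It concerns only patients on treatment at amendment 07 with unknown HBV status. Their number is not given; the illustration puts the wider on-treatment group at roughly 3 to 8 of 300, subject to the assumed start date and to PFS standing in for time on treatment. Sample size, error rates and efficacy analyses are unaffected. It should still be corrected, because the test feeds a rule for holding study treatment and addresses the risk that prompted the amendment.

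**What to change.** In footnote h, delete the condition on the DNA test and the undefined marker with it. State that HBsAg, anti-HBsAb, anti-HBcAb (total and IgM) and HBV DNA are each tested once in every on-treatment patient of unknown HBV status, and repeated if clinically indicated, in agreement with Section 8.2.5.

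If the sponsor prefers reflex testing, the same conditional rule must appear in both places. It must also include HBsAg-negative, anti-HBc-positive patients; otherwise the resolved-infection and reactivation definitions cannot be applied.

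The first option costs one footnote edit. The few DNA assays it adds relative to the footnote are already required by Section 8.2.5.

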1.3 PHARMACOKINETIC/PHARMACODYNAMIC FLOW CHART

IPd arm only

Study phase	Treatment phase																		End of treatment (EOT)	Post treatment Follow-up period			
	Cycle 1						Cycle 2			Cycle 3		Cycle 4			Subsequent cycles		30 ±5 days after last study treatment	60 ±5 days after last study treatment		Monthly (±7 days) for approximately 12 months			
Day	D1			D8	D15			D22	D1			D15		D1					D15		D1	D15	
Time (decimal hours)	0h Start Infusion	EOI	EOI +1h	0h Start infusion	0h Start Infusion	EOI	0h Start Infusion	0h Start Infusion	EOI	0h Start Infusion	0h Start Infusion	0h Start Infusion	0h Start Infusion	EOI	EOI +1h	0h Start Infusion	0h Start Infusion	0h Start Infusion					
Indicative clock time	8 am	12 pm	1 pm	8 am	8 am	12 pm	8 am	8 am	12 pm	8 am	8 am	8 am	8 am	8 am	12 pm	1 pm	8 am	8 am	8 am	8 am	8 am	8 am	
Treatment																							
isatuximab (IV infusion)	X-----	---X		X	X-----	---X	X	X-----	---X	X	X	X	X	X-----	---X		X	X	X				
Pharmacokinetics ^e																							
isatuximab	P00 ^a	P01 ^b	P02 ^c	P03 ^a	P04 ^a	P05 ^b	P06 ^a	P00 ^a	P01 ^b	P02 ^a	P00 ^a	P01 ^a	P00 ^a	P01 ^b	P02 ^c	P03 ^a	P00 ^a				PF0		
Pharmacodynamics ^e																							
ADA (Immunogenicity) ^f	P00 ^a				P01 ^a			P00 ^a				P00 ^a					P00 ^a				PF0	PF1 ^d	PFX ^d

^a Sample collected (within 10 min) strictly before the start of isatuximab infusion (ie, after administration of the isatuximab premedications).

^b Sample collected just before actual end of infusion (EOI). A time window of [±10 min] around the actual end of infusion will be allowed for end of infusion sample.

^c Sample collected 1 hour [±10 min] after the actual end of infusion.

^d At 60 days, if patient is positive or inconclusive for ADA, additional ADA are required every 30 days (±7 days) until sample is negative (sample ID: PF2, PF3 etc).

^e Refer to laboratory manual for sample collection, processing and shipping.

^f The sampling times for ADA detection can be modified based on the updated knowledge of isatuximab on immunogenicity. For patients still on treatment at the time of amended protocol 07, sample is no more required.

If isatuximab is stopped prior to pomalidomide and dexamethasone, ADA will be tested on D1 of the 2 next cycles. If ADA test at the second cycle administered without isatuximab is positive or inconclusive, ADA testing will be repeated every cycle until negative.

After the PFS cut-off date, no further PK samples will be collected.

EOI = End of Infusion; ADA = Anti-Drug Antibody (immunogenicity); P = Plasma; 1 Cycle = 28 days.

3 LIST OF ABBREVIATIONS

ADA:	antidrug antibodies
ADCC:	antibody-dependent cellular-mediated cytotoxicity
AEs:	adverse events
AESI:	adverse event of special interest
ALT:	alanine aminotransferase
ANC:	absolute neutrophil count
ASCO:	American Society of Clinical Oncology
ASCT:	autologous stem cell transplantation
AST:	aspartate aminotransferase
AT:	all treated
AUC:	area under the curve
BM:	bone marrow
BMA:	bone marrow aspirate
cADPR:	cyclic adenosine-diphosphate-ribose
CBR:	clinical benefit rate
CDC:	complement-dependent cytotoxicity
CI:	confidence interval
CID:	clinical important difference
CLL:	chronic lymphocytic leukemia
CR:	complete response
DMC:	Data Monitoring Committee
DOR:	duration of response
DVT:	deep vein thrombosis
ECOG:	Eastern Cooperative Oncology Group
ELISA:	enzyme linked immunoabsorbant assay
EORTC:	European Organisation for Research and Treatment of Cancer
EOT:	end of treatment
ePROs:	electronic patient reported outcomes
EQ-5D-5L:	European Quality of Life Group questionnaire with 5 dimensions and five levels per dimension
FCBP:	female of child-bearing potential
FISH:	fluorescence in situ hybridization
FPI:	first patient in study
GVHD:	graft versus host disease
HBcAb:	hepatitis B core antibody
HBsAb:	hepatitis B surface antibody
HBsAg:	hepatitis B surface antigen
HBV:	hepatitis B virus
HDAC:	hystone deacetylase
HLA:	human leukocyte antigen
HLGT:	high level general term

HLT:	high level term
HRQL:	health-related quality of life
HSC:	hematopoietic stem cell
IAR:	infusion associated reaction
ICF:	informed consent form
IEC:	independent ethics committee
IFN:	interferon
IL:	interleukin
IMiDs:	immunomodulatory drugs
IMWG:	International Myeloma Working Group
IPd:	isatuximab pomalidomide dexamethasone
IRB:	institutional review board
IRC:	Independent Response Committee
IRT:	interactive response technology
ITT:	intent-to-treat
IV:	Intravenous
kDa:	kilodalton
KIR:	killer cell inhibitory receptor
mAb:	monoclonal antibody
MedDRA:	Medical Dictionary for Regulatory Activities
MM:	multiple myeloma
MR:	minimal response
MRD:	minimal residual disease
NAD+:	nicotinamide adenine dinucleotide
NCI-CTCAE:	National Cancer Institute Common Terminology for Adverse Event
NK:	natural killer
NSAIDs:	non steroid anti-inflammatory drugs
ORR:	overall response rate
OS:	overall survival
PBMC:	peripheral blood mononuclear cells
Pd:	pomalidomide dexamethasone
PD:	progressive Disease
PDy:	pharmacodynamic
PE:	pulmonary embolism
PFS:	progression free survival
PIs:	proteasome inhibitors
PK:	pharmacokinetic
PR:	partial response
PRO:	patient reported outcome
PT:	preferred term
QLQ-C30:	quality of life questionnaire with 30 questions
QLQ-MY20:	EORTC myeloma module with 20 items
RBC:	red blood cell
RRMM:	relapsed refractory multiple myeloma
SAE:	serious adverse event
SC:	Steering Committee

SCT:	stem cell transplant
SOC:	system organ class
SPD:	sum of the products of the maximal perpendicular diameters of measured lesions
TEAE:	treatment-emergent adverse event
TLS:	tumor lysis syndrome
TNF:	tumor necrosis factor alpha
TTP:	time to progression
UPEP:	Urine Protein immunoelectrophoresis
URTI:	Upper Respiratory Tract Infection
VAS:	visual analogic scale
VGPR:	very good partial response
WBC:	white blood cell

4 INTRODUCTION AND RATIONALE

4.1 INTRODUCTION

CD38 is a Type II glycosylated 45 kilodalton (kDa) membrane protein that was identified as a lymphocyte marker (2). CD38 has a role in leukocyte homeostasis through modulation of hematopoietic cell survival and differentiation (3). CD38 functions as a receptor binding to CD31 and is involved in cell adhesion and signal transduction. The function of CD38 in signal transduction appears to be versatile depending on the cell lineage, the differentiation stage, and, possibly, the association with different co-receptors (3). CD38 is also an ecto-enzyme catalyzing the synthesis and hydrolysis of cyclic adenosine-diphosphate-ribose (cADPR) from nicotinamide adenine dinucleotide (NAD⁺) to ADP-ribose (4). These reaction products are implicated in calcium mobilization and intracellular signaling (5).

The expression of CD38 in healthy humans can be detected on natural killer (NK) cells, monocytes, dendritic cells, macrophages, granulocytes, activated T and B cells, and plasma cells. In contrast, expression has not been detected in hematopoietic stem cells (HSC), resting T and B cells, or tissue macrophages. Several hematological malignancies express CD38 including those of B-lymphocyte, T-lymphocyte and myeloid origin. Moreover, CD38 was identified as a negative prognostic marker in some hematological malignancies, such as chronic lymphocytic leukemia (CLL). The expression of CD38 is especially notable in multiple myeloma (MM) as >98% of patients are positive for this protein (6, 7). The strong and uniform expression of CD38 on malignant clonal MM cells contrasts with the restricted expression pattern on normal cells suggesting this antigen may be useful for specific targeting of tumor cells.

